
Institutions with patients waiting that are unable to use the Portal should alert the CTSU Regulatory Office immediately at [REDACTED] to receive further instruction and support.
	
Contact the CTSU Help Desk with any OPEN related questions by phone or email : [REDACTED] [REDACTED]
	

Contact the CTSU Regulatory Help Desk at [REDACTED] for regulatory assistance.
		

The most current version of the study protocol and all supporting documents must be downloaded from the protocol-specific page located on the CTSU members' website [REDACTED] Access to the CTSU members' website is managed through the Cancer Therapy and Evaluation Program - Identity and Access Management (CTEP-IAM) registration system and requires log in with a CTEP-IAM username and password.
		

Permission to view and download this protocol and its supporting documents is restricted and is based on person and site roster assignment housed in the CTSU Regulatory Support System (RSS).
		

For clinical questions (i.e. patient eligibility or treatment-related) see the Protocol Contacts, Page 2.
		

For non-clinical questions (i.e. unrelated to patient eligibility, treatment, or clinical data submission)
 
Contact the CTSU Help Desk by phone or e-mail: CTSU General Information Line – [REDACTED] All calls and correspondence will be triaged to the appropriate CTSU representative.
		

**IMPROVING SURGICAL CARE AND OUTCOMES IN OLDER CANCER PATIENTS THROUGH
IMPLEMENTATION OF AN EFFICIENT PRE-SURGICAL TOOLKIT (OPTI-SURG)**

[figure not shown]
Patient Eligibility Criteria: (See [Section 3.1](#))

- Patients must have known or suspected cancer diagnosis and have one of the following cancer-directed operations planned: Gastrectomy; Colectomy; Proctectomy; Esophagectomy; Pancreatectomy; Hepatectomy; Total cystectomy; Partial or Total Nephrectomy; Lung resection (wedge resection, segmentectomy, lobectomy, or pneumonectomy)
- Age \geq 70 years
- Patients with known metastatic disease with a plan for curative intent resection are eligible.
- Patients with double primaries undergoing planned curative operation for both are eligible.
- Patients undergoing emergent surgery are not eligible.
- Patients under active treatment for second primary are not eligible.
- Patients with known metastatic disease who are undergoing palliative resection are not eligible.

1.0 BACKGROUND

1.1 Introduction

The number of older adults who undergo major surgery is expected to double from 7 million to 14 million by 2030.¹ Frailty, an age-related decline in physiologic reserve, is present in least half of older adults who undergo elective surgery.²⁻⁴ There is strong evidence that components of frailty—functional and cognitive impairment, malnutrition, depression, and social vulnerability—put patients at risk for complications, mortality, prolonged length of stay, discharge to an institution and not home, functional decline, and poor quality of life.³⁻¹⁰ Mounting evidence indicates that multimodal interventions aimed at optimizing vulnerabilities associated with frailty before surgery result in decreased complications, enhanced functional recovery, increased discharge to home, reduced length of stay, and decreased hospital cost.¹¹⁻¹⁴ Recently published best practices guidelines for the optimal care of the geriatric surgical patient released by the American Geriatrics Society and the American College of Surgeons state that these vulnerabilities should be identified and optimized preoperatively.¹⁵ In current surgical practice, however, routine screening for or attempt to address these vulnerabilities before surgery is not performed. Screening tools are perceived to be cumbersome and primary surgical providers are not equipped to directly address the uncovered vulnerabilities. The goal of the proposed study is to evaluate the implementation of an efficient tool in surgical practices that can *detect and optimize* the components of frailty before surgery.

1.2 Current state of knowledge and clinical/care delivery practice

Well-coordinated perioperative and practice-based interventions can improve older patients' functional status after surgery but few surgical practices have implemented these strategies. A recent survey of surgical oncologists reported that although the majority of surgeons expressed interest in preoperative optimization for older patients, only 6% of them currently perform geriatric assessments in their older patients.¹⁶ Factors contributing to the low level of adoption include perceptions regarding the amount of time required to assess for vulnerabilities and lack of specific programs designed to address them within typical surgical oncology practices. This project focuses on implementing an efficient tailored tool to determine the potential for a package toolkit that identifies and addresses geriatric vulnerabilities preoperatively to affect the delivery of surgical cancer care to elderly frail patients. Moreover, we will determine which practice-change strategies effectively integrate these interventions into routine delivery. Practice facilitation and quality improvement methods have been shown to be effective in improving implementation of guidelines and evidence based practices (EBP).¹⁷ Practice facilitation has been defined as “a process of interactive problem solving and support that occurs in a context of a recognized need for improvement and a supportive interpersonal relationship.”³¹ Within practice facilitation, quality improvement methods are used to facilitate the implementation of the new EBP, such as the plan-do-study-act (PDSA) cycles from the Institute for Healthcare Improvement model. For practice facilitation, we will use a centralized implementation coach to assist practices to implement the pre-surgical optimization intervention. Prior research also shows that tailoring interventions to account for variance in practice culture can improve intervention uptake and effectiveness. Our study design thus focuses not only on assessing the effectiveness of an efficient tool on improving outcomes for patients, but also on assessing the cultural climate in which practice facilitation and care delivery improvement efforts are deployed.

Frailty and surgical outcomes in cancer patients: Frailty is common in older adults presenting for surgery. Emerging data indicates that frailty, compared to advanced age alone, is more strongly associated with morbidity and mortality after surgery.⁶⁻⁸ Although published studies

often use different instruments to measure frailty, the overwhelming majority of studies have found that frailty is associated with complications, early and late mortality, prolonged length of stay, poor functional recovery, discharge to an institution, and lower quality of life.³⁻¹⁰ Cancer surgery among frail older adults is associated with a 3 to 4-fold increase in both 30-day post-operative complications and mortality.^{7,10} An analysis of SEER-Medicare showed an 11 item frailty measure was associated with a 10-fold increase in 90-day mortality following colorectal surgery.⁸

Evidence supports multimodal optimization to improve functional outcomes before major surgery: Studies evaluating preoperative optimization of a single domain of vulnerability (e.g., nutrition or fitness) have had mixed results.¹⁴ However, multimodal interventions that address multiple vulnerabilities have demonstrated impressive results.^{12,13} In a study of elderly patients undergoing colorectal surgery, 81% of older patients who were enrolled in a trimodal prehabilitation program, including protein supplementation, anxiety reduction, and an exercise program, had returned to baseline function at 8 weeks compared with only 40% in the pre-intervention control group.¹³ In another before-and-after study of the effect of pre-operative comprehensive geriatric assessment and multimodal prehabilitation education (home exercise, nutrition, relaxation techniques, and pain management), outcomes were significantly improved among patients who underwent the intervention (pneumonia, 4% post-intervention period vs 20% pre-intervention period; delirium, 6% post-intervention period vs 19% pre-intervention period; and length of stay, 12 days post-intervention period vs 16 days pre-intervention period).¹² A recent single center study of older patients undergoing thoracic and abdominal surgery demonstrated that preoperative program consisting of exercise, nutritional supplementation, and stress management education significantly reduces hospital costs and length of stay.³⁰ Multimodal interventions aimed at modifying frailty traits are likely to yield the most benefit in older patients.

1.3 Preliminary Data

Our group at the UCSF Center for Surgery in Older Adults developed a program to identify and optimize frail patients prior to major surgery. Pilot implementation of the Edmonton Frail Scale (EFS) in our clinic showed that it required the following administration time: by first-year medical students mean 10.1/median 9.5 minutes, range 6-16 minutes. During the pilot phase, our team which includes a surgeon, geriatrician, occupational therapist, physical therapist, and dietitian, developed and refined written materials and resource guides to support optimization of frailty before surgery. Materials were developed in an iterative approach incorporating feedback from a patient and family advisory panel and older surgical patients preparing for surgery.

For practices randomized to Arm 2, see also, Appendix III; for practices randomized to Arm 3, see also Appendix X.

1.4 Contribution to cancer care delivery

Major surgery in frail older adults often results in complications, death, functional decline, loss of independence, affecting quality of life and causing significant resource burdens to patients, families, and health care systems. Older adults with limited life-expectancy often value function and independence over potential gains in life-expectancy.¹⁹ Surgical care pathways that assess and attempt to optimize frailty traits before surgery will enhance functional recovery for frail cancer patients and ensure that frail adults who undergo major cancer surgery achieve their treatment goals and maintain independence. To implement frailty screening and optimization into diverse surgical practices, a robust study is needed that tests an efficient screening and optimization tool and addresses clinical culture and barriers to implementation in a broad variety

of clinical settings. If feasible and effective on the practice level, the OPTI-Surg toolkit will improve the delivery of cancer surgery and quality of life for frail older adults in the U.S.

This study will inform care and improve outcomes for frail older adults who undergo major cancer surgery. If successful, this study will demonstrate that implementation of frailty screening is feasible in a busy clinic setting, acceptable to clinic staff, and that practice-based implementation of OPTI-Surg improves functional recovery in frail older adults and reduces post-operative morbidity. Furthermore, this trial has the potential for broad impact for cancer care delivery by serving as a model for testing and implementing practice-based interventions aimed at improving surgical outcomes not only among frail older adults but for patients with a variety of conditions.

1.5 Study design

We plan a cluster randomized trial to evaluate the effectiveness of practice-level implementation of OPTI-Surg. Practices will be randomized to the OPTI-Surg package intervention alone, OPTI-Surg with an implementation coach, or usual care. Interventions at the practice level are most likely to result in standardized approaches to patient evaluation and management with the highest likelihood of successful broad-based implementation. Randomization by practice will also prevent contamination. The comparison of coach versus no-coach arms will provide data on which practice change strategies are effective while ensuring that strategies are feasible and acceptable. Through this study design, we will both evaluate the effectiveness of the OPTI-Surg intervention to improve surgical outcomes at the patient level, but we will also gain further insight on the effectiveness of implementing this intervention at the practice level. We will gain knowledge about the implementation process as practices implement the OPTI-Surg Toolkit in order to better understand how practice level interventions should be conducted. Our design also includes direct measurement of practice culture and intervention roll-out through mixed methods (surveys, observation, and qualitative interviews). These mixed-methods data will identify barriers to implementation and acceptability, inform continuous improvement of the intervention, and provide insights into how to tailor the intervention to individual practice sites to ensure effective dissemination.

Study population: The target of intervention will be surgical practices. The study will include evaluation of patients, providers, and practice organizational and structural factors. Practices will be randomized to utilize the OPTI-Surg package intervention alone, OPTI-Surg with an implementation coach, or usual care. Eligible practices will be engaged in elective cancer operations that are high risk in older adults. Based on administrative data on operative mortality, the following have been identified as high risk in older adults: Gastrectomy 3-10%; colectomy 1-2%; proctectomy 2%; esophagectomy 6-16%; pancreatectomy 2-10%; hepatectomy 3-7%; nephrectomy 2%; total cystectomy 3%; and lung lobectomy/pneumonectomy 3-9%.¹⁹ Eligible practices will have a high prevalence of patients among whom there is a high risk of frailty and be categorized as either a thoracic, major abdominal, or urologic practice. Prior research has shown that > 50% of patients aged 70+ presenting for major surgery are frail.⁶ Based on this data, patients included in the study will be (a) age \geq 70 years who are presenting for surgical evaluation for (b) one of the noted high risk procedures (listed above). To address the variation in expected functional recovery by procedure type, we plan to stratify randomization by three practice types: (1) thoracic, (2) major abdominal, and (3) urologic. Esophagogastric procedures may be included in either the thoracic or major abdominal surgery categories, depending upon the specialty of the operating surgeon.

Endpoints: This study will incorporate both patient-level and site-level data collection. For patient-level data collection, individual eligible patients will be approached for participation and

will sign a consent form for completion of questionnaires preoperatively—at baseline prior to surgery or optimization intervention—and at 8 weeks after surgery.

For site-level data collection, data collection will consist of chart review and will include all eligible patients within the practice during the duration of the study. The primary study endpoint (patient-level data) is the function level 8 weeks after surgery. Physical function will be measured preoperatively at baseline and 8 weeks after surgery using the Community Healthy Activities Model Program for Seniors (CHAMPS) questionnaire. CHAMPS includes 41 questions that ask the senior to estimate the time spent on a range of activities. Among older adults with limited life-expectancy, function and independence are highly valued. A major goal of preoperative optimization of frailty traits is to improve baseline function and mitigate social vulnerability so that functional recovery is accelerated after surgery. The secondary endpoints (site-level data) are post-operative morbidity (grade I or higher surgical complications) and penetration of OPTI-Surg administration (i.e., screening rate among eligible patients) in the OPTI-Surg alone and OPTI-Surg plus coaching arms. Proctor and colleagues defined penetration as the “integration of a practice within a service setting and its subsystems.”²¹ Penetration will be calculated as the number of older adults administered the OPTI-Surg, divided by the total number of older adults eligible for OPTI-Surg.

1.6 Goals

The goal of this study is to improve the delivery of surgical cancer care in OPTI-Surg to identify vulnerabilities and promote targeted interventions to improve outcomes. This cluster-randomized trial will assess the effectiveness of the OPTI-Surg package within the NCORP community oncology research programs. The **primary goal** is to improve 8-week postoperative function among elderly patients through incorporation of a practice level targeted pre-surgical geriatric intervention. 8-week post-operative function will be compared between the combined OPTI-Surg arms versus the usual care arm. We hypothesize that among surgical practices that employ the frailty assessment and intervention, patient-reported function 8 weeks after surgery will be higher than the usual care sites.

Secondary goals are to assess the potential of the OPTI-Surg toolkit to decrease postoperative morbidity. We hypothesize that among surgical practices that employ the OPTI-Surg intervention, a lower proportion of patients will experience postoperative complications. We also seek to assess and compare the penetration of the OPTI-Surg within surgical practices between arms with and without an implementation coach. We will assess practice level rates of completion of the brief assessment for all older surgical patients and compare them between sites randomize to either no coach or coach.

We also hope to learn about how practice level changes can be implemented to impact global outcomes in the real-world setting. We will:

- 1) Assess the impact of the OPTI-Surg toolkit on postoperative mortality, length of hospital stay, discharge to a facility, and hospital readmission. Mortality, length of hospital stay, discharge to a facility, and hospital readmissions will be compared between the *combined* OPTI-Surg arms versus the usual care arm.
- 2) Assess subsequent referral for the indicated optimization intervention and assess practice-level structural factors associated with penetration of the OPTI-Surg package. We hypothesize that OPTI-Surg implementation rates will vary depending on the available resources and capacity and the presence or absence of stakeholder buy-in, but that it can be influenced by the presence of an implementation coach.

- 3) Explore the acceptability, feasibility, and appropriateness of the intervention (Section 10) [More information for institutions randomized to OPTI-Surg arms is provided in Appendices III and X.].
- 4) Document and assess barriers and facilitators to implementation through mixed-methods research. To facilitate interpretation of the trial results and to facilitate future dissemination and implementation, we propose to use mixed-methods (qualitative and quantitative) to collect and analyze data. To collect quantitative data, we will use a validated survey, the Organizational Readiness to Change Assessment (ORCA), to assess practice readiness and identify potential barriers or challenges.²²

Qualitative data will be collected during site visits with selected study sites. These in-depth ethnographic case studies will occur at a total of 12 Alliance sites – 2 usual care sites, 5 sites with the OPTI-Surg intervention only, and 5 sites that have the OPTI-Surg intervention plus the coach. The site visit will include observation of everyday clinic processes and interviews with clinic leaders, staff, and front-line workers. Site visits will be conducted before, during, and after the implementation of the OPTI-Surg intervention in order to examine barriers and facilitators to implementing the intervention. Specifically, we will plan site visits at the 12 case-study sites at the following three points in time: 1) a **baseline** site visit will occur before the OPTI-Surg intervention has been introduced at the site; 2) an **in-progress** site visit will occur after OPTI-Surg intervention has been implemented and while it is still active; we will schedule this visit after the 5th patient has been recruited and ensure that the site visit occurs before enrollment at the site is complete; 3) a **post-intervention** visit will occur 6-9 months after the final (15th) patient has been recruited at the study site; this visit will assess what, if any, lasting impact OPTI-Surg appears to have had on practice culture and routines at the site.

2.0 OBJECTIVES

2.1 Primary objective

To compare 8-week postoperative function among elderly patients between sites randomized to implement the OPTI-Surg toolkit with or without a coach versus sites randomized to usual care.

2.2 Secondary objectives

2.2.1 To compare postoperative morbidity between sites randomized to implement the OPTI-Surg toolkit with or without a coach versus sites randomized to usual care.

2.2.2 To compare the penetration of the OPTI-Surg toolkit between sites randomized to implement the OPTI-Surg toolkit with a coach versus sites randomized to implement the OPTI-Surg toolkit without a coach.

2.3 Exploratory objectives

2.3.1 To compare postoperative mortality, hospital length of stay, discharge to a facility, and hospital readmission between sites randomized to implement the OPTI-Surg toolkit with or without a coach versus sites randomized to usual care.

2.3.2 To assess subsequent initiation and follow through of appropriate referral for the indicated optimization intervention and assess practice-level structural factors associated with uptake of the OPTI-Surg package.

2.3.3 To document and assess barriers and facilitators to implementation and dissemination through mixed-methods research.

3.0 PATIENT SELECTION

For questions regarding eligibility criteria, see the Study Resources page. Please note that the Study Chair cannot grant waivers to eligibility requirements.

3.1 Eligibility Criteria

- **3.1.1 Eligible patients must have known or suspected cancer diagnosis and have one of the following cancer-directed operations planned:**
 - Gastrectomy
 - Colectomy
 - Proctectomy
 - Esophagectomy
 - Pancreatectomy
 - Hepatectomy
 - Total cystectomy
 - Partial or Total Nephrectomy
 - Lung resection (wedge resection, segmentectomy, lobectomy, or pneumonectomy)
- **3.1.2 Age \geq 70 years**
- **3.1.3 Patients with known metastatic disease with a plan for curative intent resection are eligible** (e.g., curative liver resection for metastatic colorectal cancer).
- **3.1.4 Patients with double primaries undergoing planned curative operation for both are eligible** (e.g., synchronous colon cancers undergoing colectomy to treat both).
- **3.1.5 Patients undergoing emergent surgery are not eligible.**
- **3.1.6 Patients under active treatment such as chemotherapy, targeted therapy, immunotherapy, radiation treatment, etc. for second primary, are not eligible.** However, patients not currently receiving treatment are eligible, including patients who have been previously treated for another cancer. Patients are not considered to have a “currently active” malignancy if they have completed therapy and are free of disease for \geq 2 years.
- **3.1.7 Patients with known metastatic disease who are undergoing palliative resection are not eligible.**
- **3.1.8 Patients with psychiatric illness or other mental impairment that would preclude their ability to give informed consent or to participate in the prehabilitation program are not eligible.**
- **3.1.9 Patients must be able to speak and complete questionnaires in English.**

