4.3.3 Intervention-specific appendices

In order to maintain institutional blinding with respect to OPTI-Surg interventions, information specific to the OPTI Surg arms is provided separately in Appendices III and X. Following randomization, practices should contact [REDACTED] [REDACTED] [REDACTED] to obtain the appendices specific to the intervention arm to which the practice has been randomized. The OPTI-Surg Toolkit/Manual will also be provided to sites at this time.

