7.0 STUDY IMPLEMENTATION

7.1 Eligible Practices

Eligible practices will be engaged in elective cancer operations that are high risk in older adults. Based on administrative data on operative mortality, the following have been identified as high risk in older adults: gastrectomy 3-10%; colectomy 1-2%; proctectomy 2%; esophagectomy 6-16%; pancreatectomy 2-10%; hepatectomy 3-7%; nephrectomy 2%; total cystectomy 3%; and lung lobectomy/pneumonectomy 3-9%.

Eligible practices will have a high prevalence (at least 10 cases per year) of patients among whom there is a high risk of frailty (age ≥ 70 years old) and be categorized as either a thoracic, major abdominal, or urologic practice. Practices should identify a clinical research professional, allied health professional, or equivalent to implement OPTI-Surg.

Eligible practices should provide a brief description of any existing programs for frailty assessment and intervention. If their current practice includes the assessment and interventions specified in the protocol, they will be ineligible.

See Section 4.3.1 for information regarding site approval procedures.

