7.5.1 Usual Care

These practices will not get the OPTI-Surg intervention. Practices randomized to usual care will complete the practice demographic and structural survey and the ORCA questionnaire at baseline (i.e., as soon as the practice site agree to participate and before training) and at 6, 12, and 24 months following site activation. Two practices randomized to usual care will also undergo staff interviews at baseline, after the fifth patient is enrolled, and 6 to 9 months after the last patient is enrolled to the study at the practice.

For all patients (consented and unconsented) aged ≥ 70 years, practices will keep a log of all patients seen. The practice will submit the log monthly. In addition, the practices will submit data abstracted from patient charts. Practices will report surgical complications for all eligible patients. The log will be a spreadsheet format of the case report form variables.

The CHAMPS and EQ-5D-5L questionnaires will be administered to consenting eligible patients at the time of the initial surgical consultation and 8 weeks after surgery.

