8.1 Electronic Medical Review (EMR)

[Additional information for practices randomized to Arm 2 or Arm 3 can be found in Appendix III and Appendix X, respectively.]

All eligible patients at all participating institutions will be identified using EMR monthly and as needed to screen patients for participation. Eligibility of all patients whether consenting to participate in the questionnaire portion of the study or not will be determined. Surgical complications will also be recorded for all patients.

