12.4.3 Secondary and exploratory analysis

A generalized linear mixed model (with logit link function) with a random practice effect to account for clustering within practice will be used to compare postoperative complications within 12 weeks of surgery between the combined OPTI-Surg no-coach and coach arms versus usual care followed by pairwise comparisons. This analysis will also include all eligible elderly patients who undergo major cancer surgery (no documentation of postoperative complications will be considered as not having any postoperative complications). A generalized linear mixed model (with logit link function) with a random practice effect to account for clustering within practice will also be used to compare compliance rate for screening between the no-coach and coach arms. This analysis will include all eligible elderly patients with planned major cancer surgery. Generalized linear mixed models (with appropriate link function based on the distribution of the outcome variable being compared) with a random practice effect to account for clustering within practice will be used to compare other surgical outcomes within 12 weeks of surgery and to compare EQ-5D-5L index and visual analog scale scores between the combined OPTI-Surg no-coach and coach arms versus usual care. Models for EQ-5D-5L scores will include the respective baseline EQ-5D-5L score as a covariate. In supplemental analysis, we will compare outcomes and EQ-5D-5L index and visual analog scale scores pairwise between arms (coach vs usual care, no-coach vs usual care, and coach vs no-coach) using the same method. Supplemental analysis will also incorporate patient and practice characteristics which appear to differ among randomization arms.

A variety of supplemental and exploratory analyses will be conducted primarily using descriptive analysis as well as model-based analysis (where applicable and supported by adequate sample size) including to describe the frequency of interventions implemented and to explore the relationship between site characteristics and likelihood of compliance.

With the addition of the virtual EFS effective with Update #03 to the study, we will additionally explore whether outcomes differed according to EFS used (in-person vs. virtual).

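### The prehabilitation limb of criterion 3.1.8 can be applied unevenly by arm when practices define the all-eligible set for complications versus usual care

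*Combined protocol and SAP*

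**What the plan says.** **The criterion.** Section 3.1.8 covers psychiatric illness and other mental impairment. Patients in whom this would "preclude their ability to give informed consent or to participate in the prehabilitation program are not eligible". There are two limbs, consent and prehabilitation, in one text with no arm qualifier. The supplied text does not define the program.

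**Who has the program.** Section 7.5.1 says of usual care: "These practices will not get the OPTI-Surg intervention". Section 7.1 keeps out practices that already have an equivalent: "If their current practice includes the assessment and interventions specified in the protocol, they will be ineligible". Section 4.3.3 places the arm-specific content in Appendices III and X, obtained after randomization, and gives the reason: "In order to maintain institutional blinding with respect to OPTI-Surg interventions".

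**Who judges eligibility, and for what.** Section 8.1 has each practice review records monthly and as needed: "Eligibility of all patients whether consenting to participate in the questionnaire portion of the study or not will be determined". For complications, compared between the combined OPTI-Surg arms and usual care, section 12.4.3 says: "This analysis will also include all eligible elderly patients who undergo major cancer surgery". Death, length of stay, discharge to a facility and readmission come from the same chart review (10.3.1).

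**Penetration.** Section 10.1 defines it only within the OPTI-Surg arms, and 12.4.3 compares it only between no-coach and coach.

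**The concern.** An entry rule is safe in a cluster trial with recruitment after assignment only if every arm can apply it in the same way. An OPTI-Surg practice can ask whether a patient's mental state rules out the program it delivers. A usual-care practice has to guess at a program it neither runs nor has been given.

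The limb also overlaps with what the intervention looks for. Section 1.1 lists the components of frailty as "functional and cognitive impairment, malnutrition, depression, and social vulnerability". In the order of section 8, frailty assessment (8.2) comes before consent (8.3), and its content is given only to Arms 2 and 3. Those practices may learn of impairments that usual care never records.

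At stake is the complications comparison, together with mortality, length of stay, discharge and readmission. Complications could also become the main result: section 12.4.4 moves the emphasis to it if more than 30% of primary data are missing. Later repair is hard, because 13.1.1 has data on non-consenting patients collected de-identified and in aggregate.

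**Working it through.** **1. What the plan states.** The plan gives no complication rate, no power for complications and no share of patients failing 3.1.8, so there is no plan figure to reproduce for this comparison. The nearest one is 85% power for penetration (12.3: 60% against 80%, 11 evaluable patients per practice). A simulation with 10 practices per arm, a cluster effect of 0.005 assumed to apply to screening, and a t-test on practice proportions gives 86.4%. That figure is sound and does not bear on this point.

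**2. Bias in complications with no true effect.** Assumed inputs:
- x: share of all-eligible patients failing only the prehabilitation limb, all dropped in the OPTI-Surg arms and all kept in usual care
- p0: complication rate in everyone else
- RR: risk in the x group relative to everyone else

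OPTI-Surg rate = p0. Usual-care rate = (1 − x)·p0 + x·RR·p0. Spurious difference D = x·p0·(RR − 1).

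| x | p0 | RR | D (points) | Spurious odds ratio |
|---|---|---|---|---|
| any | any | 1 | 0 | 1.00 |
| 1% | 30% | 1.5 | 0.01 × 30 × 0.5 = 0.15 | 0.993 |
| 5% | 30% | 1.5 | 0.05 × 30 × 0.5 = 0.75 | 0.965 |
| 5% | 40% | 1.5 (60% risk) | 0.05 × 60 + 0.95 × 40 − 40 = 1.0 | 0.959 |
| 10% | 40% | 1.5 (60% risk) | 0.10 × 60 + 0.90 × 40 − 40 = 2.0 | 0.921 |
| 10% | 30% | 2 | 0.10 × 30 × 1 = 3.0 | 0.870 |
| 10% | 50% | 2 | 0.10 × 50 × 1 = 5.0 | 0.818 |

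The last row is an outer bound: RR 2 on a 50% base means every such patient has a complication. D shrinks roughly in proportion if usual care also drops some of the group. It changes sign if usual care drops them and OPTI-Surg keeps them.

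**3. Distance to the fallback in 12.4.4.** Section 12.3 plans 11 × 30 = 330 evaluable of 450, so 120 missing (26.7%). The threshold is 0.30 × 450 = 135. With 16 more missing, 136/450 = 30.2% exceeds it.

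**4. Penetration.** Usual care contributes no denominator. Suppose both OPTI-Surg arms removed the same share of unscreened patients. At 5%, the rates become 0.60/0.95 = 63% and 0.80/0.95 = 84%, a gap of 21 points. At 10%, they become 0.60/0.90 = 67% and 0.80/0.90 = 89%, a gap of 22 points. The planned gap is 20.

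**The case against.** **The rule is the same in every arm.** A reader might infer that arms follow different eligibility rules. They do not: there is one text. What stands is the possibility of uneven application of an undefined term.

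**The group is small.** A reader might take 3.1.8 to exclude everyone unable to do prehabilitation. It excludes only those precluded by psychiatric illness or other mental impairment. Many of them would also fail the consent limb, or 3.1.9 on completing questionnaires in English, and both of those apply in all arms. This stands: the 5 to 10% used above has no support in the documents, and the true share may be nearer the bottom of the table.

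**Usual care is not wholly in the dark.** Section 1.2 describes earlier multimodal prehabilitation studies, and the ORCA survey that usual-care staff complete names the Edmonton Frail Scale and targeted recommendations. This stands in part. Those passages convey the idea of prehabilitation, but they do not describe what OPTI-Surg asks of a patient.

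**The direction is not shown.** Because cognitive impairment and depression are targets of the toolkit, OPTI-Surg practices might keep such patients. This stands: a bias in favour of OPTI-Surg is conditional on who is dropped and on their risk.

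**Penetration.** A reader might infer that penetration is distorted in the same way, or that practices will reclassify unscreened patients as ineligible. The first cannot happen, since usual care is not in that contrast. No passage documents the second, and applied equally it moves the contrast by only 1 to 2 points.

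**Unseen text.** Appendices III and X are not in the supplied text and may define the program. Usual care would still not receive that definition.

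**Conclusion.** The point holds for complications and the other chart-review outcomes compared with usual care. One arm cannot apply the prehabilitation limb on the same footing as the others, and eligibility is judged by practices that know their arm, so differential selection is possible.

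Its size cannot be derived from the documents. Under the assumptions shown it runs from 0 through 0.15 points and 1 to 2 points to an outer bound of 5 points. It favours OPTI-Surg only if higher-risk patients are dropped in those arms and kept in usual care. A larger chart-review sample would not reduce it.

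The primary CHAMPS comparison is restricted to consenting patients and is outside this point, as is the penetration contrast. This is an inexpensive improvement to a secondary comparison that could become the main one, not a flaw that invalidates the design.

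**What to change.** Leave 3.1.8 as written for the consented questionnaire cohort. Deleting the limb there would admit patients who could not receive the program and dilute the primary comparison.

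In 8.1 and 12.4.3, state that the prehabilitation limb is not applied when defining the all-eligible chart-review set for complications and the other surgical outcomes, so that the set rests only on criteria that can be charted identically in every arm.

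In the log of patients aged 70 or over (7.5.1), record for each patient whether 3.1.8 would exclude them and by which limb, so that counts can be reported by arm. Section 7.5.1 describes this log for usual care; confirm that Arms 2 and 3 keep the same one. As a sensitivity analysis, report the result with the patients flagged under the prehabilitation limb excluded, which shows how much the limb matters.

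The cost is a short amendment, one extra log field, a few more charts to abstract, and slight dilution of any effect by patients who could not take part in the program.
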